9.4.4 SAFETY ANALYSES

Safety data will be presented by treatment group to the Data and Safety Monitoring Board during the course of the trial. Each adverse event will be displayed showing AE name per the CTCAE v5.0 when applicable, class, severity, patient ID, clinic, treatment group, time since randomization, resolution status and physician's assessment of relatedness to treatment. Patient-specific summary tables including any adverse event (yes vs no), frequency of multiple adverse events (i.e., 0, 1, 2, 3+) and highest severity of adverse event (none, mild, moderate, severe, life-threatening) will be displayed by treatment group along with p-values from Fisher's exact tests.

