1.2 SCHEMA

1.3 DATA COLLECTION SCHEDULE (DCS)

Assessment/Procedure	Screening Visits		Follow-up visits Weeks from Randomization						
	S	RZ	F04	F08	F12	F24	F28	F36	F48
Consent and reaffirmation	X	X
Baseline medical history	X
Follow-up medical history (with AUDIT-C)	.	.	X	X	X	X	X	X	X
Alcohol Use Disorders Identification Test (AUDIT)	X
Lifetime Drinking History (Skinner)	X
Review for adverse effects	.	.	X	X	X	X	X	X	X
Review for concomitant medications	X	X	X	X	X	X	X	X	X
Drug dispensing	.	X
Review of study drug adherence	.	.	X	X	X	X	.	.	.
Detailed* (D) or Focused† (F) physical exam	D	.	F	F	D	D	F	F	D
NASH CRN Liver Symptom Questionnaire	X	.	X	X	X	X	X	X	X
Cardiovascular risk factor assessment	X	X	.	.	X
Beverage Intake Questionnaire (BEVQ-15)	X	X	.	.	X
FibroScan®: liver stiffness and steatosis (CAP)	X	X	.	.	X
Complete blood count (CBC) ‡	X	X	.	.	X
Basic metabolic panel (BMP) §	X	X	.	.	X
Fasting lipid profile¶	X	.	.	.	X	X	.	.	X
Hepatic panel** and GGT	X	.	X	X	X	X	X	X	X
Fasting glucose and insulin	X	.	X	X	X	X	X	X	X
Prothrombin time (PT), activated Partial Thromboplastin Time (aPTT), and INR	X	X	.	.	X
HbA1c	X	X	.	.	X
C-reactive protein (CRP)	X	.	.	.	X	X	.	.	X
Pregnancy test	X	X	.	.	.
Prostate Specific Antigen (PSA) Test††	X	X
Banking‡‡: Fasting serum, plasma	X	.	.	.	X	X	.	.	X
Etiologic tests§§	X
Closeout form	X

* **Detailed physical exam:** anthropometric assessments (body weight [kg], body height [cm], waist circumference [cm], and hip circumference [cm]); vital signs (temperature, heart rate, respiratory rate, blood pressure), organ systems (skin, chest, lungs, heart, abdomen, nervous); liver signs and changes in bleeding (e.g. bleeding gums).

† **Focused physical exam:** anthropometric assessments (body weight [kg], body height [cm], waist circumference [cm], and hip circumference [cm]); vital signs (temperature, heart rate, respiratory rate, blood pressure); liver signs and **changes in bleeding (e.g. bleeding gums)**. The focused physical exam may be completed remotely via telemedicine video call per institutional guidelines.

‡ **Complete blood count:** hemoglobin, hematocrit, mean corpuscular volume (MCV), white blood cell count (WBC), red blood cell count (RBC), platelet count

§ **Basic metabolic panel:** glucose, calcium, sodium, potassium, CO₂ (carbon dioxide, bicarbonate), chloride, blood urea nitrogen (BUN), creatinine. eGFR will be calculated using the CKD-EPI formula.

¶ **Fasting Lipid profile:** total cholesterol, triglyceride, LDL, HDL.

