2.3 RISK/BENEFIT ASSESSMENT

2.3.1 KNOWN POTENTIAL RISKS

Risks of vitamin E: Vitamin E at 533.6 mg (800 IU) daily dose (the maximum dose for this study) has no significant toxicity in adults [71, 72]. Side effects of long-term use of vitamin E in excess of 400 to 800 IU/day may include: diarrhea, nausea, flatulence, stomach cramps, weakness, dizziness, headache, fatigue, and blurred vision [73]. Long-term use of supplemental vitamin E has also been associated with an increased risk of bleeding, specifically gingival bleeding [74]. While some studies have shown no effect of vitamin E on

biomarkers of bleeding (eg. prothrombin time)[75, 76], vitamin E use has been associated with increased bleeding tendencies in vitamin K deficient patients, which is very rare in adults without specific underlying conditions (e.g. cystic fibrosis, biliary obstruction) [73]. In one study, vitamin E supplementation was associated with prostate cancer in men [56]. Additionally, one meta-analysis suggested that doses of vitamin E >400 IU/day were associated with an increase in all-cause mortality[55]. However, this analysis has been criticized, as explained in section 2.2, and at least one subsequent meta-analysis has failed to demonstrate a relationship between vitamin E supplementation and all-cause mortality [57].

Blood drawing: Blood draw may cause mild discomfort, such as swelling, temporary sensation of pain, burning, or a bruise that may develop and last for a few days. Less common risks include a blood clot at the site of puncture, swelling of the vein and surrounding tissues, and possible bleeding from the puncture site. Very rarely, fainting, blood clots, or an infection at the site can occur. During the entire study period (up to 56 weeks), subjects will have approximately 20 tablespoons of blood drawn (300 mL).

Study visits: This study requires approximately 9 visits to the study center (screening visit, randomization visit, and 7 post randomization visits) which may cause some inconvenience to some individuals.

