2.3.3 ASSESSMENT OF POTENTIAL RISKS AND BENEFITS

Rationale for necessity of exposing participants to risk and minimization of risks: Risks to patients in this study include that vitamin E (d-alpha-tocopherol) may cause increased bleeding, diarrhea, nausea, flatulence, stomach cramps, weakness, dizziness, headache, fatigue, or blurred vision with prolonged use. Risks are minimized by exclusion of patients with higher than normal risk of bleeding and by close monitoring. Risks are

also minimized in this trial by using ALT as a surrogate marker of histologic response, thus avoiding the need for repeat liver biopsies in this phase 2 study.

Justification of the risks: All participants will receive standard of care treatment as part of the trial and will potentially benefit if they are in a treatment group (133.4 mg, 266.8 mg, or 533.6 mg of vitamin E) by improvement in ALT. The value of identifying a minimal effective dose for vitamin E in NAFLD is high because vitamin E has been shown to be effective in NAFLD at high doses (533.6 mg per day), but if a lower dose can be used effectively, potential long term adverse effects may be avoided. By conducting the trial and furthering the understanding of vitamin E for adult NAFLD, all of the participants in the study stand to benefit in the future if the minimum effective dose of vitamin E is identified.

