8.2 SAFETY AND OTHER ASSESSMENTS

Assessments for Safety

- **Physical examination** (e.g., height, weight, waist and hip measurements, vital signs (temperature, heart rate, respiratory rate, blood pressure), liver symptoms, gingival/orocutaneous bleeding; petechiae.
- **Laboratory results** – All labs including creatinine (and calculated GFR) potassium levels and bicarbonate will be monitored at sites and in the central database and all abnormal values will be managed by the site investigator.
- **Bleeding risk** – Participants will be evaluated for bleeding risk throughout the study using physician examination, laboratory results of prothrombin time, activated Partial Thromboplastin Time (aPTT), and INR, and patient self-report.
- **Concurrent use of anticoagulant** – Participants will be questioned about use of any anticoagulants, including aspirin, throughout the study.

Biological specimen collection and laboratory evaluations – There will be consistent methods throughout the study to ensure comparison. ALT will be measured at each site and the same lab at each site will be used for the measurement at baseline, 24 week and 48 week visits. Other local labs may be used, if necessary, when completing an allowable remote visit (see section 8.1.4.1), and will be noted in the data system. **Follow up of Ongoing Adverse Events**

Provisions for follow up of adverse events include phone calls by the coordinators to assess symptoms, in person follow up exams when needed to assess vital signs and physical findings and referral to local ongoing care by the patient's primary care physician or hospital when needed.

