8.3.8 EVENTS OF SPECIAL INTEREST

N/A

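### No bleeding-specific or coagulation and platelet comparison by arm is pre-specified, and the pooled adverse-event tests have little ability to show a dose-related bleeding effect

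*Combined protocol and SAP*

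**What the plan says.** Section 2.3.1 names the risk: "Long-term use of supplemental vitamin E has also been associated with an increased risk of bleeding, specifically gingival bleeding". Section 2.3.3 puts bleeding first in its list of risks and states the mitigation: "Risks are minimized by exclusion of patients with higher than normal risk of bleeding and by close monitoring". The concern runs through the design:

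- Section 5.2 excludes anticoagulant users, people with clotting disorders and people with platelets below 150,000/mm³.
- Section 6.3 makes serious bleeding a condition for possible unmasking.
- Section 7.1 interrupts study drug on any sign of increased bleeding.
- Section 8.2 has its own entry: "Participants will be evaluated for bleeding risk throughout the study using physician examination, laboratory results of prothrombin time", with aPTT, INR and self-report also listed.

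On data, the schedule in section 1.3 has a row for "Prothrombin time (PT), activated Partial Thromboplastin Time (aPTT), and INR". With the visit descriptions in 8.1.4, this puts coagulation tests and the blood count (which includes platelets) at screening, week 24 and week 48. PSA is taken in males at screening and week 48.

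On analysis, section 9.4.4 displays each adverse event by name, class and treatment group. The tables that carry a test are "Patient-specific summary tables including any adverse event (yes vs no), frequency of multiple adverse events (i.e., 0, 1, 2, 3" or more), and worst severity, by Fisher's exact test. The section headed "8.3.8 EVENTS OF SPECIAL INTEREST" is marked N/A. The secondary endpoints in sections 3 and 9.1 include the frequency of all CTCAE events, but no bleeding, coagulation, platelet or PSA variable. Section 8.3.5 gives the DSMB adverse-event rates by group. Section 10.1.6 names hepatotoxicity, not bleeding, for quarterly review by masked group.

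**The concern.** Section 2.3.3 justifies the search for a minimum effective dose on the ground that "if a lower dose can be used effectively, potential long term adverse effects may be avoided". That argument needs efficacy by dose and harm by dose. Efficacy gets dose-versus-placebo estimates and 95% intervals. For bleeding, the risk the protocol manages most visibly, no estimate by dose is planned. The planned tests pool all adverse events, so a few extra bleeds are diluted by common unrelated events. A null any-event table could then be read as evidence of no dose-related harm. If bleeding terms and laboratory contrasts are chosen only after unmasking, the choice is open to the criticism that the results guided it.

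**Working it through.** **Inputs.** From the documents (section 9.2): four arms of 50, with 10% missing, so 45 evaluable per arm (50 × 0.9). The documents state no bleeding rate, adverse-event rate or safety power, so there is no figure of the plan's own to reproduce. All rates below are assumptions.

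**1. Any-event table.** Let *b* be the rate of other adverse events, independent of bleeding, and *p* the bleeding rate. Then P(any event) = 1 − (1 − *b*)(1 − *p*). With *b* = 60% and *p* = 2/4/8/16% at placebo/200/400/800 IU, this gives 60.8/61.6/63.2/66.4%. An eightfold rise in bleeding moves the any-event rate by under 6 points.

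Power at the two-sided 5% level by simulation (4,000 to 6,000 trials), with a four-arm Fisher test and an exact conditional trend test with scores 0 to 3:

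| Bleeding by arm | Any-event Fisher, *b* = 40% to 90% | Bleeding Fisher | Bleeding trend |
|---|---|---|---|
| 2/4/8/16% | 11% falling to 5% | 61% | 76% |
| 1/2/4/8% | 6% falling to 4.5% | 27% | 43% |
| 2/3/5/8% | 6% falling to 5% | 17% | 26% |
| 2/3/4/6% | 6% falling to 5% | 9% | 15% |

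Repeat runs differ by one or two percentage points. The any-event test is never far from its 5% false-positive rate.

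**2. Secondary event-frequency endpoint.** This is analysed by Poisson regression, each dose against placebo. Assume one event per bleeder, no overdispersion and a background mean of *m* events per person. Bleeding of 16% against 2% adds a difference of 0.14, with SE = √[(2*m* + 0.18)/50].

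- *m* = 1: SE 0.209, z = 0.67, power about 10%.
- *m* = 1.5: SE 0.252, z = 0.56, power about 9%.
- *m* = 3: SE 0.352, z = 0.40, power about 7%.

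The false-discovery adjustment over 48 p-values can only lower these. This endpoint dilutes bleeding in the same way.

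**3. What 50 per arm can show for bleeding.** Against 0/50, pairwise Fisher needs 6/50 (p = 0.027; 5/50 gives 0.056). Against 1/50 it needs 8/50 (p = 0.031). By Newcombe's method, 8/50 against 1/50 is a difference of 14 points, 95% CI about 3 to 27. For 4/50 against 1/50 it is 6 points, CI about −4 to 17, with Fisher p = 0.36. In the second case the interval shows that a material excess is not excluded, which the p-value alone hides.

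**4. Week 24 coagulation values.** With 45 per arm and baseline correlation ρ, SE = SD × √[(2/45)(1 − ρ²)], and the shift detectable with 80% power is 2.80 × SE. For ρ = 0.3, 0.5 and 0.7 (assumed) this is 0.56, 0.51 and 0.42 SD. Such a contrast is feasible, and none is planned.

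**5. PSA.** Section 2.3.1 states: "In one study, vitamin E supplementation was associated with prostate cancer in men". Section 2.2 gives an excess of 1.6 per 1,000 person-years in the cited prevention trial, at 400 IU/day. For 150 treated participants over 24 weeks, 150 × 24/52 = 69 person-years, and 69 × 1.6/1,000 = 0.11 excess cancers, even if all were male. The only follow-up PSA is at week 48, 24 weeks after treatment ends. A formal PSA test is not worth planning.

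**The case against.** Safety by arm is not ignored. Section 9.4.4 displays every event by name and arm, and its list of tables is not exhaustive. Section 8.3.5 promises comparisons of event rates by group, section 10.1.6 lets the DSMB ask for more, and section 8.2 has laboratory values monitored centrally as well as at sites. The secondary event-frequency endpoint already yields dose-versus-placebo estimates with intervals. This rules out the reading that safety, or bleeding, goes unanalysed. What remains is narrower: a listing is not an incidence with a difference and an interval, the DSMB comparison specifies no bleeding grouping, the formal comparisons pool all causes, and nothing compares coagulation or platelets after baseline.

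A reader might also infer that bleeding is the main known harm, or that the week 24 coagulation result is the only objective evidence. The documents support neither. Section 2.3.1 also names prostate cancer and a disputed mortality signal, reports no significant toxicity at 800 IU, and cites studies finding no effect on prothrombin time. Bleeding signs are examined at every follow-up visit.

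The strongest objection concerns yield. Bleeding-prone patients are excluded, so a steep gradient may be optimistic, and at 2/3/5/8% even the specific tests would usually miss the effect. Nor can 24 weeks of treatment estimate long-term harm. Both stand. They limit what the added analysis can claim and favour estimates over tests, but they do not make the pooled tables informative about bleeding.

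**Conclusion.** The gap is real and moderate. No bleeding-specific, PT, aPTT, INR or platelet comparison by arm is pre-specified, although the protocol builds exclusions, drug holds and an unmasking condition on bleeding and collects the data. Under the assumed rates, the any-event Fisher test has about 4% to 11% power. A bleeding comparison has about 61% to 76% for the steep gradient and 17% to 26% for 2/3/5/8%. These figures rest on assumed bleeding and background rates, and on independence between bleeding and other events. It would be wrong to infer that the added tests would reliably detect a bleeding effect; their value lies in a stated estimate and interval per dose. The primary efficacy inference and individual participant monitoring are unaffected.

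**What to change.** Add to section 9.4.4, in the safety analysis dataset:

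(a) The number and percentage of participants per arm with any bleeding adverse event, from a list of CTCAE terms fixed before unmasking, plus bleeding SAEs. Give each dose-versus-placebo difference with a 95% CI and one exact dose-trend p-value labelled descriptive. Include this table, by masked group, in the DSMB's existing report.

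(b) Week 24 PT, INR, aPTT and platelets by ANCOVA on the baseline value, each dose against placebo with a 95% CI, plus counts shifting from normal to abnormal. State how many participants per arm were off drug at week 24, because the bleeding hold in section 7.1 may have interrupted treatment in some of those affected.

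(c) PSA change in males, summarised descriptively only.

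The cost is a short analysis amendment, agreement on the term list and a few extra tables. No visit or blood draw is added, and no dose, hold or stopping rule changes. The downside is some unadjusted safety p-values, to be labelled as such.

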9.2 SAMPLE SIZE DETERMINATION

The primary endpoint is the relative change in ALT at week 24 from baseline [i.e., (ALT at baseline – ALT at week 24)/ALT at baseline]. There are three vitamin E treatment groups: 133.4 mg/day, 266.8 mg/day, 533.6 mg/day and one placebo group. The primary analysis is intention-to-treat analysis of minimum effective dose using Williams' test of mean 24-week relative change in ALT. If the percentage of patients with missing follow-up data on the primary endpoint is greater than 10%, multiple imputation using chained equations method with 50 imputations modeling will be used to impute missing values; otherwise complete-case analysis will be used.

Among patients in PIVENS with baseline ALT ≥ 60 U/L, the mean 24-week relative change in ALT was 40% in the vitamin E (800 IU/day) group and 20% in the Placebo group. The Mean (SD) of the vitamin E – placebo difference in relative change (%) was -20% (31%). Using this estimate as the clinically meaningful difference, the trial has 90% power to detect a significant minimum effective dose given a sample size of 200 patients (50 per group with equal allocation) given a 2-sided Type I error of 5%, missing data rate of 10% and using Williams' test for minimum effective dose (MED) (Williams 1971, Williams 1972) obtained from PASS 2019 software (PASS 2019 Power Analysis and Sample Size Software (2019). NCSS, LLC. Kaysville, Utah, USA, ncss.com/software/pass).

The testing for minimum effective dose starts by comparing the 24-week relative change in ALT in each of the 3 dose groups with the placebo group using critical values obtained from Williams' test for MED. (Critical values will be obtained using SAS PROBMCM function.) Williams' test assumes the same or increasing efficacy with increasing dose; therefore, if the mean change at a dose level is less in absolute value than the mean change in a lower adjacent dose category, the groups are combined for statistical comparison. The lowest dose that is significantly different from placebo is declared the MED. By definition, all doses greater than the MED are also significantly different from placebo.

Sample size estimates for varying sizes of the treatment effect are given below given the same assumptions as above.

24-week relative change in ALT			Sample size	
Vitamin E	Placebo	Vitamin E – Plbo	No. / group	Total
48%	20%	28%	25	100
44%	20%	24%	34	136
40%	20%	20%	50	200
36%	20%	16%	76	304

32%	20%	12%	135	540
28%	20%	8%	303	1212

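### Section 9.4.4 tests two ordered adverse-event outcomes with Fisher's exact test, which uses neither category order nor dose order and so is less sensitive to a shift towards worse outcomes

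*Combined protocol and SAP*

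**What the plan says.** Section 9.4.4 plans three patient-level safety tables by treatment group: any adverse event (yes or no), "frequency of multiple adverse events (i.e., 0, 1, 2, 3" (the last category being three or more), and highest "severity of adverse event (none, mild, moderate, severe, life-threatening) will be displayed by treatment group along with p-values from Fisher's exact tests". Fisher's test applies to all three. The section does not say whether Fisher's test is one comparison of the four arms or a set of pairwise comparisons. It plans no ordinal or dose-trend test, and neither does any other section for these tables.

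The arms are graded doses. Section 9.2 says "There are three vitamin E treatment groups: 133.4 mg/day, 266.8 mg/day, 533.6 mg/day and one placebo group", with a "sample size of 200 patients (50 per group with equal allocation").

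One further adverse-event analysis exists. Change in the frequency of CTCAE-defined adverse events to week 24 is a secondary endpoint (Sections 3 and 9.1). Section 9.4.3 assigns Poisson regression to counts, with a dispersion-corrected negative binomial model as sensitivity analysis. Each dose is compared with placebo, and p-values are adjusted for false discovery across 48 comparisons.

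**The concern.** Two of the three safety outcomes run from better to worse, and the arms run from no dose to the highest dose. Fisher's test spreads its power over every departure from equal distributions, so a steady drift to worse grades with rising dose counts no more than a haphazard scatter of equal improbability.

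The plan uses dose order for efficacy: "Williams' test assumes the same or increasing efficacy with increasing dose" (Section 9.2). It does not use it for harm, although Section 2.3.3 gives as a reason for the trial that "if a lower dose can be used effectively, potential long term adverse effects may be avoided". At stake is how readily the displayed safety p-values would respond to a real, moderate, dose-related worsening.

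**Working it through.** **No plan figure to reproduce.** The documents state no adverse-event rates, detectable effect or power for safety. The 50 per arm comes from the efficacy calculation and is taken as given.

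**Why order drops out.** With the margins fixed, a table has probability (product of row-total factorials × product of column-total factorials) / (N! × product of cell factorials). Fisher's p-value sums this over all tables no more probable than the one observed. Reordering rows or columns leaves every product unchanged, so the p-value is the same however grades or doses are arranged.

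**Alternatives.** Let R_i be the rank sum of arm i, using midranks of the ordered outcome.
- Kruskal-Wallis: H = [12/(N(N+1))] Σ R_i²/n_i − 3(N+1), corrected for ties. It uses category order but not dose order.
- Linear-by-linear trend: T = Σ s_i R_i with equally spaced dose scores s_i, two-sided. It uses both orders.

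**Assumed inputs.** 50 per arm; two-sided 5%; proportional odds. Placebo severity (none, mild, moderate, severe, life-threatening, in %):
- A: 40/35/18/6/1
- B: 50/28/16/5/1
- C: 30/35/25/8/2

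To show what an odds ratio (OR) of 2.5 means under A: the odds of no event are 0.40/0.60 = 0.667. Dividing by 2.5 gives 0.267, so 0.267/1.267 = 21% have no event at the top dose. The odds of severe or worse are 0.07/0.93 = 0.0753. Multiplying by 2.5 gives 0.188, so 0.188/1.188 = 16%, against 7% on placebo.

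**Simulated power for highest severity (%), one overall four-arm test** (A: 1,500 trials; B and C: 1,000 each; Monte Carlo standard error at 36% and 1,000 trials is √(0.36×0.64/1000) = 1.5 points):

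| Pattern of harm | Placebo | Fisher | Kruskal-Wallis | Trend |
|---|---|---|---|---|
| None | B / C | 5 / 5 | 5 / 6 | 4 / 5 |
| Steady rise, top OR 2 | B / C | 22 / 17 | 37 / 34 | 51 / 50 |
| Steady rise, top OR 2.5 | A / B / C | 35 / 37 / 36 | 56 / 56 / 58 | 74 / 74 / 75 |
| Steady rise, top OR 3 | B / C | 54 / 48 | 78 / 76 | 89 / 90 |
| Steady rise, top OR 4 | B / C | 76 / 78 | 94 / 94 | 98 / 98 |
| 800 IU only, OR 2.5 | A | 51 | 73 | 65 |
| 800 IU only, OR 3 | B / C | 69 / 69 | 87 / 90 | 81 / 82 |
| All doses equally, OR 3 | B / C | 68 / 64 | 88 / 88 | 81 / 80 |
| 400 IU only, OR 2.5 | A | 51 | 72 | 11 |

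**Event count** behaves alike. With placebo 40/25/15/20% and a steady rise to OR 2.5, power is 36% (Fisher), 57% (Kruskal-Wallis) and 74% (trend). With 800 IU only, it is 52%, 73% and 67%. Other count distributions move Fisher up to 41% and the trend test up to 77% in the steady-rise case.

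**If Fisher is meant pairwise**, 800 IU against placebo under A at OR 2.5 gives 50%, against 69% for the Wilcoxon test.

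**Any event (yes/no)** has no category order to lose. With a 50% placebo rate and a steady rise to OR 2.5, Fisher and Kruskal-Wallis both give 47%.

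**The case against.** The strongest reply is that Fisher's test is valid and conventional here, holds its level, and accompanies descriptive tables. No threshold, power claim or decision rule is attached to these p-values, and the minimum effective dose is chosen on ALT alone (Section 9.4.2). The DSMB also sees individual events and adverse-event rates by group, and can ask for further safety reports (Sections 8.3.5, 9.4.4 and 10.1.6). All of this stands, and it makes the matter one of sensitivity, not of validity.

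The count outcome also has the planned Poisson comparison with placebo. Under the count assumption above, a dispersion-corrected Poisson test of 800 IU against placebo has 61 to 70% power before the false-discovery adjustment, which would lower it. That answers much of the point for counts, though the comparison is pairwise and ignores dose order. It does nothing for highest severity.

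A reader might infer that the plan halves the chance of finding dose-related harm. The documents do not support that as a general statement. They give no rates and do not say that Fisher's test is overall. The ratio of Fisher's power to the trend test's is near one half only for moderate, steadily rising harm. It is 51/65 = 0.78 for 800 IU only at OR 2.5, about 0.8 at OR 4, and it reverses when only the middle dose does harm. Nor do the documents say that a non-significant result will be taken as no difference between doses. Section 2.3.3 speaks of long-term effects, whereas treatment here lasts 24 weeks.

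**Conclusion.** The concern holds as a loss of sensitivity in two displayed tests, chiefly that for highest severity, where Fisher's is the only test planned. For a steady rise to a top-dose odds ratio of 2.5, one overall Fisher test has about 35 to 40% power. Using category order raises this to about 56 to 61%, and using dose order as well to about 75%. These figures rest on assumed adverse-event rates, proportional odds and 50 per arm.

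Kruskal-Wallis was ahead of Fisher in every harm pattern tabulated, including harm at 400 IU only. The trend test is best for steady harm but poor alone (about 11 to 13%) if only the middle dose does harm. The change is worth making because it is cheap. The plan as it stands would still give valid descriptive p-values.

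**What to change.** In Section 9.4.4:
- Keep Fisher's exact test for any adverse event (yes/no), and say whether it is overall or pairwise.
- For highest severity and number of events, display a permutation Kruskal-Wallis test across the four arms.
- Beside it, add one prespecified two-sided ordinal dose-trend test, for example linear-by-linear on midranks with equally spaced dose scores fixed in advance.
- Label both p-values descriptive.

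The cost is SAP wording and a few lines of code, with no new data, visits or participants. The downside is one extra p-value in each of two tables. The trend test is weak for non-monotone harm, which is why Kruskal-Wallis stays beside it.
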